6.5.3 Unanticipated problems resulting in risk to participant or others.....	19
6.5.4 Adverse drug reactions.....	19
6.6 Dissemination Policy	19
Table 1: Schedule of Events	20
Table 2: Primary Outcome Analysis	21
Table 3: Secondary Outcome Analysis.....	22
Table 4: Other Secondary Outcomes Analysis.....	23
Figure 1: Femur Fracture	24
Figure 2: Tibia Fracture.....	25
Figure 3: Unblinding of Personnel for Emergency Medical Management.....	26
Figure 4: Retention Strategies	27
7.0 REFERENCES.....	28

LIST OF ABBREVIATIONS

Abbreviation	Explanation
AE	Adverse Event
ASBMR	American Society for Bone and Mineral Research
CEO	Center for Evidence-Based Orthopaedics
CDC	Centers for Disease Control and Prevention
CI	Confidence Interval
CRF	Case Report Form
CTX	C-Terminal Telopeptides of Type I Collagen
FDA	US Food and Drug Administration
FIX-IT	Function IndeX for Trauma
IRB	Institutional Review Board
PACS	Picture Archiving and Communication System
PHI	Personal Health Information
PINP	Amino-Terminal Procollagen Propeptides of Collagen Type I
PTH	Parathyroid Hormone
RCT	Randomized Controlled Trial
REB	Research Ethics Board
RUST	Radiographic Union Score for Tibial fractures
SAE	Serious Adverse Event
SD	Standard Deviation
STC	R Adams Cowley Shock Trauma Center
25(OH)D	25-hydroxy vitamin D

STUDY SUMMARY

Methodology	Phase II exploratory randomized controlled trial (RCT)
Coordinating Center	Center for Evidence-Based Orthopaedics (CEO), McMaster University, Hamilton, ON
Clinical Site	R Adams Cowley Shock Trauma Center (STC), Baltimore, MD
Primary Aim	The primary objective is to determine the effect of vitamin D ₃ supplementation on fracture healing at 3 months.
Secondary Aim	The secondary objective is to determine if 25-hydroxy vitamin D [25(OH)D] serum levels are associated with fracture healing at 3 months.
Other Secondary Objective	The other secondary objective is to confirm study protocol feasibility for a larger definitive phase III efficacy RCT to determine the optimal vitamin D ₃ dosing regimen to reduce re-operations for fracture healing complications in healthy adult patients.
Diagnosis and Main Inclusion Criteria	Healthy adults ages 18-50 years with non-osteoporotic femoral or tibial shaft fractures who are treated with intramedullary fixation will be enrolled. Only acute fractures will be eligible.
Treatment Groups and Study Products	Each participant will be randomized to 1 of 4 treatment groups: 1) 150,000 IU loading dose vitamin D ₃ plus daily dose placebo; 2) loading dose placebo plus 4,000 IU vitamin D ₃ per day; 3) loading dose placebo plus 600 IU vitamin D ₃ per day; or 4) loading dose placebo plus daily dose placebo. All doses of vitamin D ₃ supplements/placebo will be provided in a blinded manner. The daily treatment will commence within 1 week of injury and will be taken for 3 months. The loading dose vitamin D ₃ supplements/placebo will be given within 1 week of injury and at 6 weeks post-injury. All doses of vitamin D ₃ and the placebo will be obtained from Bio-Tech Pharmacal, Inc. (Fayetteville, AK).
Length of Follow-Up	The primary outcome will be assessed at 3 months post-fracture. Participants will be followed for 12 months.

Study Outcomes
	
Fracture healing (primary outcome) will be assessed as follows: 1) clinical fracture healing will be measured using the Function IndeX for Trauma (FIX-IT), 2) radiographic fracture healing will be measured using the Radiographic Union Score for Tibial fractures (RUST), and 3) biological fracture healing will be measured using serum levels of cross-linked C-terminal telopeptides of type I collagen (CTX) and amino-terminal procollagen propeptides of collagen type I (PINP).
 
The secondary outcome will be assessed by measuring 25(OH)D serum levels. Correlations will be assessed between participants' 25(OH)D levels at enrolment, changes in 25(OH)D levels from enrolment to 3 months, and 25(OH)D levels at 3 months and fracture healing as described above.
 
The other secondary outcomes will include assessing supplementation adherence between daily and loading doses, confirming participant safety as measured by adverse events (AEs) and serum levels of calcium and parathyroid hormone (PTH), and assessing protocol adherence (e.g. completion of outcome assessment and participant follow-up).

Sample Size
	
96 patients will be included.

1.0 INTRODUCTION

Vitamin D supplements are increasingly being recommended to healthy adult fracture patients without an osteoporotic injury.¹ Although this is a relatively new practice pattern, the basis for this adjunct therapy is grounded in the high hypovitaminosis D prevalence rates (up to 75%) among healthy adult fracture patients,¹ and the strong biologic rationale for the role of vitamin D in fracture healing.²⁻⁶ Briefly, experimental animal studies have demonstrated that the concentration of vitamin D metabolites is higher at a fracture callus compared to the uninjured contralateral bone,³⁻⁵ vitamin D supplementation leads to decreased time to union and increased callus vascularity,² and increases mechanical bone strength compared to controls.⁶ While evidence to confirm that vitamin D supplementation improves fracture healing in clinical studies does not exist, the pre-clinical data are compelling and worthy of further investigation.

With modern orthopaedic surgical care, rates of complications following tibia and femoral shaft fractures can be as high as 15%. Complications, including delayed union, nonunion, or infection often require secondary surgical procedures⁷⁻⁹ and result in profound personal and societal economic costs.¹⁰⁻¹² While surgeons continue to seek advances in surgical technique, it is becoming increasingly obvious that innovations in orthopaedic techniques or implants are unlikely to eliminate complications.¹³ As a result, considerable attention is currently focused on adjunct biologic therapies, such as vitamin D.¹⁴⁻¹⁶

A recent survey of 397 orthopaedic surgeons showed that only 26% routinely prescribe vitamin D supplementation to adult fracture patients.¹⁷ Of the 93 surgeons who indicated that they routinely prescribe vitamin D supplementation, 29 different dosing regimens were described ranging from low daily doses of 400 IU to loading doses of 600,000 IU.¹⁷ This suggests a high level of clinical uncertainty surrounding the use and optimal dose of vitamin D supplementation in adult fracture patients. If vitamin D supplementation improves fracture healing outcomes, then there is a large opportunity to increase its use; however, before widespread adoption occurs, research is needed to optimize the dosing strategy, establish the dosing safety in the immobilized fracture healing population, and overcome potential medication adherence issues among the often-marginalized patients that suffer trauma.

The long-term goal of our research program is to conduct a large phase III RCT to determine which dose of vitamin D₃ supplementation optimally improves acute fracture healing outcomes in healthy adult patients (18-50 years). The current proposed phase II exploratory trial will perform important preliminary work to test the central hypothesis that vitamin D₃ dose and timing of administration is critical for improving fracture healing at 3 months. This trial will also inform the feasibility of the large phase III RCT. This trial is registered at clinicaltrials.gov (Identifier number: NCT02786498).

2.0 STUDY AIMS AND OBJECTIVES

2.1 Primary Aim

The primary aim is to assess the effect of vitamin D₃ supplementation on fracture healing at 3 months. Fracture healing will be assessed as follows: 1) clinical fracture healing will be measured using the Function IndeX for Trauma (FIX-IT),¹⁸ 2) radiographic fracture healing will be measured using the Radiographic Union Score for Tibial fractures (RUST),^{19–22} and 3) biological fracture healing will be measured using serum levels of cross-linked C-terminal telopeptides of type I collagen (CTX) and amino-terminal procollagen propeptides of collagen type I (PINP).²³

2.2 Secondary Aim

The secondary aim is to determine if 25(OH)D serum levels are associated with fracture healing at 3 months.

2.3 Other Secondary Objective

The other secondary objective is to confirm study protocol feasibility for a larger definitive phase III efficacy RCT to determine the optimal vitamin D₃ dosing regimen to reduce re-operations for fracture healing complications in healthy adult patients.

2.4 Hypotheses for the Primary and Secondary Objectives

Primary Objective: Lower extremity shaft fractures heal via callus formation and secondary bone healing. This seminal process begins within a few weeks of injury and vitamin D metabolites have been extensively implicated in this stage of healing. During these early weeks, circulating vitamin D levels are most likely to be critical to bone healing; therefore, we hypothesize:

- 1) *High doses (loading or daily) will increase healing compared to low daily dose.* Using high doses will rapidly increase the circulating vitamin D available during fracture callus formation.
- 2) *High loading dose increases healing compared to high daily dose.* Loading doses will overcome medication adherence issues and increase circulating vitamin D even more rapidly than daily doses.
- 3) *Low daily dose will increase healing compared to placebo.* While the low daily dose is not expected to increase circulating vitamin D as rapidly as the high dose strategies, this comparison will determine if rapid serum increases are necessary to improve fracture healing.

Secondary Objective: Based on experimental data and the role of vitamin D on bone metabolism, a correlation between circulating vitamin D levels and fracture healing is expected; however, the efficacy of various supplementation strategies may be dependent on the patient's baseline vitamin D status or other related changes. For example, it is known that the dose response of supplementation varies depending on the patient's serum 25(OH)D levels, with larger increases seen in patients with serum levels <20ng/ml.

3.0 METHODS

3.1 Study Setting

This study will be coordinated jointly by the University of Maryland, R Adams Cowley Shock Trauma Center (STC), Baltimore, MD and McMaster University, Center for Evidence-Based Orthopaedics (CEO), Hamilton, ON. Patients will be enrolled from the STC. The CEO will be responsible for the protocol, data management, and data analysis.

3.2 Eligibility Criteria

The inclusion criteria are: 1) adult men or women ages 18-50 years; 2) closed or low grade open (Gustilo type I or II) tibial or femoral shaft fracture;²⁴ 3) fracture treated with a reamed, locked, intramedullary nail; 4) acute fracture (enrolled within 7 days of injury); and 5) provision of informed consent. Fifty years was selected as the upper age limit to minimize potential confounding with post-menopausal endocrine changes that affect bone metabolism. For the purposes of the study, femoral shaft fractures will be defined as any injury in which the majority of fracture line is distal to the lesser trochanter and proximal to the distal metaphyseal flare of the femoral condyles (**Figure 1**). Intertrochanteric extension or distal articular extension is permitted. Similarly, a tibial shaft fracture will be defined as an injury with a primary fracture line between the proximal meta-diaphyseal flare to the distal metaphyseal region ending one joint width proximal to the tibial plafond (**Figure 2**). Intra-articular extension is permitted.

The exclusion criteria are: 1) osteoporosis; 2) stress fractures; 3) elevated serum calcium (>10.5 mg/dL); 4) atypical femur fractures as defined by American Society for Bone and Mineral Research (ASBMR) criteria;²⁵ 5) pathological fractures secondary to neoplasm or other bone lesion; 6) patients with known or likely undiagnosed disorders of bone metabolism such as Paget's disease, osteomalacia, osteopetrosis, osteogenesis imperfecta etc.; 7) patients with hyperhomocysteinemia; 8) patients with an allergy to vitamin D or another contraindication to being prescribed vitamin D; 9) patients currently taking an over the counter multivitamin that contains vitamin D and are unable or unwilling to discontinue its use for this study; 10) patients who will likely have problems, in the judgment of the investigators, with maintaining follow-up; 11) pregnancy; 12) patients who are incarcerated; 13) patients who are not expected to survive their injuries; and 14) other lower extremity injuries that prevent bilateral full weight-bearing by 6 weeks post-fracture.

Patients with multiple injuries or multiple tibial and femoral shaft fractures will be eligible for inclusion; however, only the most severe eligible fracture will be included (as determined by the treating surgeon using the grade of soft tissue injury using the Tschernie classification system for closed fractures²⁶ and the Gustilo classification system for open fractures).²⁴

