3.6.2 Post-operative rehabilitation

Full weight-bearing as tolerated is recommended for all isolated tibial and femoral shaft fractures. In the presence of additional lower extremity fractures, intra-articular extension, or other concomitant soft tissue injuries, participants may be restricted to protected weight-bearing (partial or no weight) for up to 6 weeks post-fracture. If additional contralateral injuries are present, both limbs must be eligible for full weight-bearing by 6 weeks post-fracture.

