3.7 Primary and Secondary Outcome Measures

3.7.1 Primary outcome

Fracture healing will be assessed as follows: 1) clinical fracture healing will be measured using FIX-IT, 2) radiographic fracture healing will be measured using the RUST, and 3) biological fracture healing will be measured using serum levels of CTX and PINP.

Clinical Healing: FIX-IT is a standardized measure of weight-bearing and pain in patients with lower extremity fractures, specifically tibia and femur fractures.¹⁸ Preliminary validation of the FIX-IT has demonstrated high inter-rater agreement and moderate correlation with the physical scores of the Short Form-36.¹⁸ It has been used in other studies to assess clinical fracture healing.

Radiographic Healing: The RUST score assesses the presence of bridging callus or a persistent fracture line on each of 4 cortices.¹⁹⁻²² This score has been previously validated and found to have greater inter-rater reliability when compared with surgeons' general impression of the cortical bridging.¹⁹⁻²² RUST has been widely used to assess radiographic fracture healing.¹⁹⁻²² An orthopaedic surgeon who is independent of the study will review the images and assign a RUST score.

Biological Healing: CTX is a bone-resorption marker and previous research has found that it rises 1 week after fracture of the tibial shaft and remains elevated throughout fracture healing.²³ PINP is a bone-formation marker and prior research has found that it is highest at 12 weeks after fractures of the tibial shaft and proximal femur.³²

The primary time point for assessing fracture healing will be at 3 months post-injury. This time point was selected because it coincides within the standard clinical follow-up schedule, and because it has the greatest potential to detect differences in short-term fracture healing. While we expect the 1-year fracture union rate to be approximately 95% for the femur fractures³² and 75% for the tibia fractures (unpublished data from the SPRINT trial),⁷ improved early fracture healing is biologically plausible. The median time to fracture union for tibia fractures is 4 months; therefore, many patients are still experiencing morbidity from their injury at the 3-month visit and decreasing the time to union would be an important patient benefit.

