4.0 STATISTICAL PLAN

4.1 Sample Size Determination

This trial will use a phase II randomized screening design to facilitate non-definitive comparisons of three vitamin D₃ dosing regimens. Using the principles outlined by Rubinstein et al, the statistical parameters have been carefully chosen to ensure a reasonable sample size and meaningful results.⁴² Consistent with previous recommendations, an α and β of 0.20 was chosen with a target mean difference of 17-20%, depending on the fracture healing measure. There will be no adjustments for multiple testing given the exploratory nature of the study design.

Based on the original instrument development and validation in tibia and femur fracture patients, it is expected that the low dose and control groups will have a mean 3-month FIX-IT score of 8 (standard deviation (SD) 3).¹⁸ Assuming the high dose groups will achieve a mean 2 point increase (17% mean difference), 21 patients are required in each group. The same sample size requirements will be applied for comparisons using the RUST instrument based on similar assumptions and recent literature (2 point mean difference, 8 vs. 6, SD 3).¹⁹⁻²² Clinically important changes in the PINP and CTX markers are unknown; however, in a previous study of tibia fracture healing, Veitch et al observed concentrations of both bone turnover markers approximately 100% greater than baseline values.⁴³ Given the large changes observed in these bone turnover markers, the same criteria will be applied for identifying a potentially clinically beneficial regimen and remain powered to detect a mean difference of 20% (SD 30%). Finally, the sample size will be increased to account for a 10% loss to follow-up, for a total enrolment of 24 patients per allocation group (96 total).

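### Serum CTX and PINP do not isolate the index fracture in participants with several fractures, and the marker analyses do not allow for this

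*Combined protocol and SAP*

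**What the plan says.** Section 3.2 opens the trial to patients with other injuries: "Patients with multiple injuries or multiple tibial and femoral shaft fractures will be eligible for inclusion". For these patients "only the most severe eligible fracture will be included", so the unit of study is one bone. Exclusion criterion 14 in the same section removes only other leg injuries that would rule out full weight-bearing on both sides by 6 weeks. Section 3.6.2 expects further leg fractures among those enrolled.

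Section 3.7.1 makes serum markers part of the primary outcome: "biological fracture healing will be measured using serum levels of CTX and PINP". It describes both as responding to fracture. On resorption it says "CTX is a bone-resorption marker and previous research has found that it rises 1 week after fracture of the tibial shaft". PINP, the formation marker, is described so: "it is highest at 12 weeks after fractures of the tibial shaft and proximal femur". Twelve weeks is about the 3-month primary time point.

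Section 3.4 stratifies on open versus closed and tibia versus femur only. Section 4.2.1 and Table 2 specify independent t-tests at alpha 0.20. Section 4.2.2 relates 25(OH)D to the same markers by univariate analysis. The only sensitivity analysis is the as-treated one in Section 4.2.4. Section 3.7.4 collects injury details and fracture characteristics at baseline, but the statistical plan gives them no role.

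**The concern.** RUST is read on the index bone. A blood level cannot be confined to one bone. Because the protocol describes CTX and PINP as rising after fractures, and PINP after fractures at different sites, a participant with a second healing fracture can be expected to contribute turnover from both. The documents do not say this outright, but it follows closely from Section 3.7.1.

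Two things are at stake. First, the markers are labelled as healing of the study fracture, and in these participants they are a whole-patient measure. Second, the number of fractures becomes an unmodelled source of between-patient variation in two of the four primary measures, in arms of about 21 evaluable participants. The marker associations in Section 4.2.2 have the same gap. These results are meant to point to a regimen and, under Section 3.5.2, to guide the choice of control group for Phase III, so avoidable noise has a cost even in an exploratory trial.

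**Working it through.** **Inputs from Section 4.1.** Alpha 0.20, beta 0.20, marker difference 20% with SD 30%, 21 evaluable per group, 10% loss, 24 enrolled per group. Sidedness is not stated.

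**The plan's own figure.** Two-sided, the normal formula gives n = 2 × (1.2816 + 0.8416)² × (30/20)² = 20.3, so 21 per group. Then 21/0.9 = 23.3, so 24 per group and 96 in total. This reproduces the plan (a one-sided test would need 13). Exact t-test power with 21 per group is 80.4%.

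**Assumptions, because the documents give no figure.**
- p, the share with a further fracture: 20% to 40%.
- D, the marker level it adds at 3 months, on the plan's percentage scale: 25, 50 or 100 points. The top value borrows the rise that Section 4.1 quotes from a tibial fracture study, which "observed concentrations of both bone turnover markers approximately 100% greater than baseline values". It assumes that a second fracture adds in full.
- 30% is the SD among participants with an isolated fracture.

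**Formula.** SD_total = √(30² + p(1−p)D²). Example: p = 0.2, D = 100 gives √(900 + 0.16 × 10,000) = √2,500 = 50.

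**Power for a 20-point difference, 21 per arm, two-sided alpha 0.20** (the 1:1 comparisons):

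| D (points) | SD at p = 0.2 / 0.3 / 0.4 | Power at p = 0.2 / 0.3 / 0.4 |
|---|---|---|
| 0 | 30 | 80.4% |
| 25 | 31.6 / 32.1 / 32.4 | 77.3% / 76.3% / 75.8% |
| 50 | 36.1 / 37.7 / 38.7 | 69.2% / 66.3% / 64.8% |
| 100 | 50.0 / 54.8 / 57.4 | 50.6% / 46.3% / 44.3% |

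The pooled 2:1 comparison under hypothesis 1 starts from higher power (about 89% by the normal approximation) and is less exposed.

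**Chance imbalance.** An excess of 4 such participants in one arm of 21 shifts the mean difference by 4/21 × D: 4.8, 9.5 or 19.0 points for D = 25, 50 or 100. With p from 0.2 to 0.4, an excess of 4 or more in either direction occurs in 17% to 27% of comparisons, and of 5 or more in 8% to 16%. A shift above 20 points needs an excess of 5 at D = 100 (5/21 × 100 = 23.8), 9 at D = 50 (21.4) or 17 at D = 25 (20.2). An excess of 9 or more has a probability below 1%. This variation is already inside SD_total and is not a further loss.

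**Cost and gain of a covariate.** A useless indicator costs one degree of freedom and raises the variance of the difference by about 1/40, because arm and indicator correlate by chance: 30 × √1.025 = 30.4, and power is 79.7% instead of 80.4%. If the indicator captured all the added level, the net gain would run from 79.7 − 77.3 = 2.4 points (p = 0.2, D = 25) to 79.7 − 44.3 = 35.4 points (p = 0.4, D = 100).

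**Isolated fractures only.** At p = 0.2 to 0.4, 21 × (1 − p) leaves 16.8 to 12.6 per arm. Power is about 74% to 65% with SD 30% (normal approximation).

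**The case against.** The strongest reply is that nothing here is biased. Allocation is randomised, the t-test's standard error contains the extra variance, and false positives stay near the nominal alpha. Supplementation is systemic, so a marker contrast between arms is still a fair estimate of a whole-body effect, and a second healing fracture may even carry some of that effect. The comparisons are declared exploratory, and broad trauma eligibility is deliberate. All of this stands, and it limits the point to precision and specificity.

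The inputs are also soft. Prevalence has no source in the documents, the 30% SD may already include some of this variation, and the quoted 100% rise has no stated time point. At 25 points the loss is 3 to 5 points of power, which is small.

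Several stronger readings are tempting but not supported:
- A reader might infer that the markers fail to measure the index fracture. They include it, together with the others.
- A reader might infer that a few participants could move an arm's mean by more than the 20-point target, or that imbalance will probably matter. The working shows this needs an excess of at least 5 in 21 at the most extreme assumption.
- A reader might infer that the planned 20% difference and 30% SD come from the tibial fracture study. Section 4.1 cites that study for the rise only, and carries the criteria over from FIX-IT and RUST.
- A reader might extend the point fully to FIX-IT, since Section 3.6.2 says: "In the presence of additional lower extremity fractures, intra-articular extension, or other concomitant soft tissue injuries, participants may be restricted to protected weight-bearing". That restriction runs to 6 weeks at most, and exclusion criterion 14 removes leg injuries that would prolong it. Residual pain may remain at 3 months, but the effect is already restricted.

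**Conclusion.** The point holds as a matter of precision and specificity. In participants with further fractures, CTX and PINP are whole-patient values, and neither the randomisation nor the analysis accounts for that. There is no systematic bias and the tests are valid.

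The size depends on two quantities the documents do not give. Across the assumed range, power for the planned marker difference falls from 80% to between 77% and 44%. The low end needs 40% prevalence and full additivity at 100 points, so it is an upper bound on the harm. A loss near 25 points of added level would be minor. The change is worth making because it is cheap, not because the trial is unsound without it.

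**What to change.** In Section 4.2.1 and Table 2, replace the t-tests for CTX and PINP with a linear model containing treatment group and additional fracture at enrolment (none versus one or more). Take the indicator from the baseline injury details, and confirm that the form records it: Section 3.7.4 names injury details and fracture characteristics in general terms only. Add one supportive analysis limited to participants with an isolated index fracture, labelled as having a smaller n. The same indicator can enter the CTX and PINP associations in Section 4.2.2. Leave eligibility and sample size unchanged.

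The cost is wording and one degree of freedom per model, which is under 1 point of power if the covariate explains nothing. A none-or-any indicator treats a minor fracture like a second femur, so it removes only part of the variation.
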